9.3. Variables

Table 1 includes definitions and assessment periods for all study variables that will be used as eligibility criteria. The full code list can be found in ANNEX 2. ADDITIONAL INFORMATION.

Table 1. Variables Used to Determine Eligibility

Variable	Operational Definition	Role	Assessment Period
Elranatamab	Prescription claim or medical claim with a National Drug Code (NDC), Healthcare Common Procedure Coding System (HCPCS), ICD-10 code or generic name in the IP, non-IP or pharmacy setting for elranatamab	Inclusion	Index event
Teclistamab	Prescription claim or medical claim with an NDC, HCPCS, ICD-10 code or generic name in the IP, non-IP or pharmacy setting for teclistamab	Exclusion	All available data to index date

Variable	Operational Definition	Role	Assessment Period
Age	Age is greater than or equal to 18 years and is not missing	Inclusion	Index date
MM diagnosis	Medical claim in the IP or non-IP setting with an ICD-10 code for MM	Inclusion	All available data to index date
Observability	Closed-claims medical and pharmacy enrollment	Inclusion	180 days prior to index date to index date (inclusive)

Table 2 includes definitions and assessment periods for all study variables that will be used as baseline and treatment characteristics. The full code list can be found in ANNEX 2.
 ADDITIONAL INFORMATION. If applicable, the frequency and percentage of patients with missing data for each variable will be described.

Table 2. Variables Used to Determine Baseline and Treatment Characteristics

Objective	Variable	Definition	Assessment Period(s)
1	Age	Age in years (continuous)	Index date
1	Sex	Categorical sex Male Female	Index date
1	Race/Ethnicity	Categorical race and ethnicity Caucasian African American Asian or Pacific Islander Hispanic or Latino Other	Start of data availability to index date

Objective	Variable	Definition	Assessment Period(s)
		Unknown	
1	Region	Categorical region, assessed as the most recent value from index date Northeast Midwest West South	Start of data to index date
	Insurance type	Categorical insurance type, assessed as the most recent value to index date Commercial Medicaid Medicare Other Unknown	180 days prior to index date to index date
1	Location (Zip code)	Categorical zip code assessed as the most recent value from index date. The full categories will be reported during implementation.	Index date
1	Care setting	Categorical care setting for elranatamab or teclistamab administration IP Non-IP Pharmacy	Index date

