1	PIs ¹	Medical claim with an NDC, HCPCS, generic name or CPT code in the IP, non-IP, or pharmacy setting for bortezomib, carfilzomib, or ixazomib (dichotomous)	MM diagnosis to 1 day prior to index date Index date to the end of follow-up
1	IMiDs ¹	Medical claim with an NDC code or generic name in the non-IP or pharmacy setting for lenalidomide, thalidomide, or pomalidomide (dichotomous)	MM diagnosis to 1 day prior to index date Index date to the end of follow-up
1	Steroids ¹	Medical claim with an NDC, HCPCS, generic name or CPT code in the IP, non-IP, or pharmacy setting for dexamethasone, methylprednisolone, prednisone, or prednisolone (dichotomous)	MM diagnosis to 1 day prior to index date Index date to the end of follow-up
1	MAbs ¹	Medical claim with an NDC, HCPCS, generic name or CPT code in the IP, non-IP, or pharmacy setting for daratumumab, isatuximab, or elotuzumab (dichotomous)	MM diagnosis to 1 day prior to index date Index date to the end of follow-up
1	Chemotherapies ¹	Medical claim with an NDC, HCPCS, generic name or CPT code in the IP, non-IP, or pharmacy setting for	MM diagnosis to 1 day prior to index date

Objective	Variable	Definition	Assessment Period(s)
		doxorubicin hydrochloride, melphalan, bendamustine, cyclophosphamide, etoposide, or cisplatin (dichotomous)	Index date to the end of follow-up
1	Small molecule inhibitors ¹	Medical claim with an NDC, HCPCS, generic name or CPT code in the IP, non-IP, or pharmacy setting for venetoclax (dichotomous)	MM diagnosis to 1 day before index date Index date to the end of follow-up
1	Nuclear export inhibitors ¹	Medical claim with an NDC, HCPCS, generic name or CPT code in the IP, non-IP, or pharmacy setting for selinexor (dichotomous)	MM diagnosis to 1 day before index date Index date to the end of follow-up
1	Antivirals ¹	Medical claim with an NDC, HCPCS, generic name or CPT code in the IP, non-IP, or pharmacy setting for antiviral medications (dichotomous)	14 days prior to index date to 1 day prior to index date Index date to the end of follow-up
1	Antibiotics ¹	Medical claim with an NDC, HCPCS, generic name or CPT code in the IP, non-IP, or pharmacy setting for antibiotic medications (dichotomous)	14 days prior to index date to 1 day prior to index date Index date to the end of follow-up

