1	Serum immunoglobulin E (IgE)	Lab event with IGE as the test name and IU/mL as the result units (dichotomous)	180 days prior to index date to index date
		Most recent numeric value of a lab event with IGE as the test name and IU/mL as the result units (continuous)	
1	Serum immunoglobulin M (IgM)	Lab event with IGM as the test name and mg/dL as the result units (dichotomous)	180 days prior to index date to index date
		Most recent numeric value of a lab event with IGM as the test name and mg/dL as the result units (continuous)	
1	Bone marrow plasma cell percent	Lab event with bone marrow plasma cell percent as the test name and percent as the result units (dichotomous)	Most recent value recorded in the 180 days prior to index date to index date
		Most recent numeric value of a lab event with bone marrow plasma cell	

Objective	Variable	Definition	Assessment Period(s)
		percent as the test name and percent as the result units (continuous)	
1	M-Protein	Lab event with M-Spike as the test name and as the g/dL as the result units (dichotomous)	180 days prior to index date to index date
		Most recent numeric value of a lab event with M-Spike as the test name and g/dL as the result units (continuous)	

1. Variable assessed both at baseline and in follow-up

Table 3 includes definitions and assessment periods for all study variables being used as outcomes. The full code list can be found in ANNEX 2. ADDITIONAL INFORMATION. If applicable, the frequency and percentage of patients with missing data for each variable will be described.

Table 3. Key Variables of Interest

Objective	Variable	Definition	Assessment Period(s)
Treatment exposure			
2	Use of premedication	
Medical or pharmacy claim with evidence of an NDC, HCPCS, generic name or CPT code for the following premedications (dichotomous):
 
Acetaminophen
 
Dexamethasone
 
Diphenhydramine
	
Step-Up Dosing Period
 
See Section 9.7.2 for censoring criteria

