2	Reported vial size	
Reported vial size in the following categories (categorical):
 
 • Unknown vial – IP dose • 44 milligram (mg)/1.1 milliliter (mL) • 76mg/1.9mL • Missing dose/unknown dose 
For the exploratory cohort of teclistamab patients the reported vial size (categorical):
 
 • Unknown vial – IP dose • 30mg/3mL • 153mg/7mL 
Missing dose/unknown dose
	
Index date to the end of follow-up
 
Index date
 
Step-Up Dosing Period
 
Maintenance Periods
 
See Section 9.7.2 for more information on the assessment periods and censoring criteria

2	Patients with 2 or more administrations	Proportion of patients with 2 or more administrations of elranatamab during the assessment period	
Index date to the end of follow-up
 
Step-Up Dosing Period
 
Maintenance Periods
 
See Section 9.7.2 for more information on the assessment periods and censoring criteria

2	Average time between elranatamab claims	Sum of the days between claims for the index drug (continuous) divided by the total number of administrations -1 reported among patients with 2 or more administrations	Index date to the end of follow-up Step-Up Dosing Period Maintenance Periods See Section 9.7.2 for more information on the assessment periods and censoring criteria
2	Number of elranatamab claims	Total number of IP, non-IP, and pharmacy claims of the index drug during the time period based on vial size (continuous)	Index date to the end of follow-up Step-Up Dosing Period Maintenance Periods See Section 9.7.2 for more information on the assessment periods and censoring criteria
3	RAI	The ratio of the actual administrations received divided by the expected number of administrations (continuous) See Section 9.7.3 for more details.	Index date to the last administration of the index drug Step-Up Dosing Period Maintenance Periods See Section 9.7.2 for more information on the assessment periods and Section 9.7.3 for censoring criteria
3	Duration on treatment	Time in days between first and last treatment administration for the index treatment (continuous)	Index date to the end of follow-up See Section 9.7.2 for censoring criteria

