9.7.2. Treatment Exposure Outcomes

Treatment exposure outcomes include RAI and time between administrations. The assessment periods shown in Table 4 are based on the elranatamab label instructions and will be used to measure treatment and dosing-related outcomes for patients receiving elranatamab.¹⁸ These periods are also provided in Figure 2.

[figure not shown]
Table 4. Dosing Schedule and Expected Administrations and Vial Size of Elranatamab

Dosing Schedule	Time Period	Expected Administrations	Vial Size

[figure not shown]
Step-Up	Index date - Day 8	3 during Step-Up	44mg/1.1mL
Maintenance Period 1	Day 9 - Day 168	1 per week	76mg/1.9mL
Maintenance Period 2	Day 169 – Censor	1 every two weeks	76mg/1.9mL

Figure 2. Dosing Schedule for Elranatamab and Teclistamab

Elranatamab label instructions

Teclistamab label instructions

The assessment periods shown in Table 5 are based on the teclistamab label instructions and will be used to measure treatment and dosing-related outcomes for patients receiving teclistamab.¹⁹ These periods are also provided in Figure 2.

Table 5. Dosing Schedule and Expected Administrations and Vial Size of Teclistamab

Dosing Schedule	Time Period	Expected Administrations	Vial Size
Step-Up	Index date - Day 7	3	30 mg/3mL
Maintenance Period	Day 8 - Censor	1 per week	153 mg/1.7mL

Dosing outcomes (reported vial size, average time between claims, and frequency of claims) will be assessed during the above time periods regardless of whether the number of administrations during the period matches the number indicated on the label instructions. Duration on treatment will be measured from the first administration to the last administration of the index drug.

Patients will be censored at the earliest of death, next treatment (CAR-T, BsABs, bendamustine, or belantamab), the end of observability, or the latest data at the time of the specified analysis.

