ANNEX 2. ADDITIONAL INFORMATION

Variable	Role	Data Source(s)	Codes	Source
Elranatamab	Inclusion criteria	Claims data	HCPCS: C9165, J1323 NDC: 00069449401, 00069449402, 00069252201, 00069252202 ICD-10 Procedure code: XW013L9 Generic name: Elranatamab	ELREXFIO Outpatient Billing (2024) ELREXFIO Inpatient Billing (2024)
Teclistamab	Inclusion criteria (Exploratory cohort)	Claims data	HCPCS (Mapped via SEER using generic name): J9380, C9148 NDC: 57894044901, 57894045001 ICD-10 Procedure code: XW01348 Generic name: Teclistamab	Janssen Biotech (2023) SEER (2024)
Multiple Myeloma	Inclusion criteria, Outcome - HCRU	Claims data	C90.0x	ELREXFIO Outpatient Billing (2024)
Age	Inclusion criteria, Baseline characteristic - Demographic	Claims data	N/A	N/A
Sex	Baseline characteristic - Demographic	Claims data	N/A	N/A
Race/Ethnicity	Baseline characteristic - Demographic	Claims data	N/A	N/A

PFIZER CONFIDENTIAL

Redacted

Insurance type	Baseline characteristic - Demographic	Claims data	N/A	
Care setting	Baseline characteristic - Clinical	Claims data	See rows below: "Inpatient," "Outpatient," and "Emergency Department"	N/A
Hematopoietic stem cell transplantation	Baseline characteristic - Treatments	Claims data	
CPT: 38240, 38241, 38242, 38243
 
ICD-10 Diagnosis: T86.0, T86.00, T86.01, T86.02, T86.03, T86.09, T86.5, Z48.290, Z94.81
 
ICD-10 Procedure: 30240Y0, 30243Y0, 30250Y0, 30253Y0, 30260Y0, 30263Y0, 30230Y1, 30233Y1, 30240Y1, 30243Y1, 30230Y2, 30233Y2, 30240Y2, 30243Y2, 30230Y3, 30233Y3, 30240Y3, 30243Y3, 30230Y4, 30233Y4, 30240Y4, 30243Y4, 30253Y1, 30260Y1, 30263Y1, 30233X0, 30233G0, 30233G1, 30233G2, 30233G3, 30233X1, 30233X2, 30233X3, 30233X4, 30233Y0, 30243X0, 30243G0, 30243G1, 30243G2, 30243G3, 30243X1, 30243X2, 30243X3, 30243X4, 0243Y4, 30283X0, 30283G0, 30283G1, 30283G2, 30283G3, 30283X1, 30283X2, 30283X3, 30283X4, 30283Y1, 30283Y2, 30283Y3, 30283Y4
	
Chaudhry et al. (2022)
 
LeMaistre et al. (2013)

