Lymphocyte count	Baseline characteristic - Lab	Claims data	An event in the lab results table where the result_abbrev is lymphocytes count and result_units are thousand per µL	
Monocyte count	Baseline characteristic - Lab	Claims data	An event in the lab results table where the result_abbrev is monocytes count and result_units are thousand per µL	
Platelet Count	Baseline characteristic - Lab	Claims data	An event in the lab results table where the result_abbrev is platelets and result_units are thousand per µL	
ImmunoglobulinA	Baseline characteristic - Lab	Claims data	An event in the lab results table where the result_abbrev is IGA and result_units are mg per dL	
ImmunoglobulinG	Baseline characteristic - Lab	Claims data	An event in the lab results table where the result_abbrev is IGG and result_units are mg per dL	
ImmunoglobulinE	Baseline characteristic - Lab	Claims data	An event in the lab results table where the result_abbrev is IGE and result_units are IU per mL	
ImmunoglobulinM	Baseline characteristic - Lab	Claims data	An event in the lab results table where the result_abbrev is IGM and result_units are mg per dL	
Bone marrow plasma cell percent	Baseline characteristic - Lab	Claims data	An event in the GDD table where the test is bone_marrow and result_units are percent	
M-Protein	Baseline characteristic - Lab	Claims data	An event in the GDD table where the test is m-spike and result_units are mg/dL	
Use of premedication	Outcome - Dosing and Administration Patterns	Claims data	HCPSCS (Mapped via SEER [Dexamethasone only] or Athena – OHDSI using generic name): J0136, J0137, J0134, J0131, C9283, G6039, J1200, Q0163, J8540, J1100, J1094	SEER (2024) ELREXFIO Label

PFIZER CONFIDENTIAL

Redacted

			Generic names (and associated NDCs): Acetaminophen, Dexamethasone, Diphenhydramine	
Inpatient	Baseline characteristic, Outcome - HCRU	Claims data	Any event in the inpatient table or an event in the non-inpatient table where acute_subacute is “acute inpatient” or where utilization type is “professional services” and service subcategory contains the term “hospital/ip encounter”	
OP	Baseline characteristic, Outcome - HCRU	Claims data	Any event in the non-inpatient table where utilization type is outpatient and service subcategory is not “emergency dept encounter”	
ED	Baseline characteristic, Outcome - HCRU	Claims data	Any event in the non-inpatient table where utilization type is “outpatient” and service subcategory is “emergency dept encounter”	

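### Table 3 reads premedication use from drug-coded claims with no rule for inpatient dosing, so the proportion probably understates use and can shift with the inpatient share

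*Protocol*

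**What the plan says.** Use of premedication is listed in Protocol Section 9.3, Table 3, under Objective 2, which is primary. The definition is "Medical or pharmacy claim with evidence of an NDC, HCPCS, generic name or CPT code for the following premedications (dichotomous"), and the drugs are acetaminophen, dexamethasone and diphenhydramine. The window is the step-up period, which for elranatamab is "Index date - Day 8" (Section 9.7.2, Table 4). The row has no restriction by care setting and no third category.

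The Annex 2 entry gives HCPCS codes ("J0136, J0137, J0134, J0131, C9283, G6039, J1200, Q0163, J8540, J1100, J1094") and "Generic names (and associated NDCs): Acetaminophen, Dexamethasone, Diphenhydramine". It contains no ICD-10 procedure code.

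The index drug is treated differently. Its vial-size row in Table 3 has a category "Unknown vial – IP dose", separate from missing or unknown dose. Annex 2 also lists "ICD-10 Procedure code: XW013L9" for elranatamab and cites an inpatient billing guide among its sources.

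Table 2 collects "Categorical care setting for elranatamab or teclistamab administration" (IP, non-IP or pharmacy), but only at the index date, and does not link it to premedication. Section 9.8 says the protocol's codes and algorithms will be followed strictly. The limitations in Section 9.9 do not mention under-capture of drugs given in hospital.

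**The concern.** Two drugs given at the same visit are looked for by different means. Elranatamab given in hospital can be found from a procedure code alone, with its vial unknown. The premedication for that dose counts only if a claim carries a drug-level code or name. A two-level claim flag has no missing value, so premedication that was given but left no coded claim becomes a recorded non-use.

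If inpatient capture is poorer than capture elsewhere, a low proportion could be read as weak premedication practice when it partly reflects what claims can show. The study plans four quarterly refreshes and repeats every objective in a teclistamab cohort. A different inpatient share could then look like a difference in practice, even though no formal comparison is planned.

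**Working it through.** The protocol states no premedication figure, so there is nothing to reproduce. The question is how far the reported proportion can move when practice does not change.

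**Inputs.** None of these is given in the documents; all are assumptions shown over a range.
- p, true use: 95% in every setting
- s, share of patients stepped up in hospital: 20%, 50%, 80%
- c_non, chance that premedication outside hospital leaves a coded claim: 90% or 60%
- c_IP, the same chance in hospital: 0% or 50%

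**Formula.** Reported proportion = p × [s × c_IP + (1 − s) × c_non].

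Example: 0.95 × [0.2 × 0 + 0.8 × 0.9] = 68.4%.

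| c_non | c_IP | s = 20% | s = 50% | s = 80% | Non-inpatients only (p × c_non) |
|---|---|---|---|---|---|
| 90% | 0% | 68.4% | 42.8% | 17.1% | 85.5% |
| 90% | 50% | 77.9% | 66.5% | 55.1% | 85.5% |
| 60% | 0% | 45.6% | 28.5% | 11.4% | 57.0% |
| 60% | 50% | 55.1% | 52.3% | 49.4% | 57.0% |

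**Movement with setting.** The change from s = 20% to s = 80% is p × (c_non − c_IP) × 0.6. From the top row down this is 51.3, 22.8, 34.2 and 5.7 percentage points. It is zero if capture is equal in the two settings. The non-inpatient column does not depend on s.

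**Against sampling error.** The dataset held 56 patients with an elranatamab claim when the protocol's count was taken. The exact 95% interval for 28 of 56 is 36% to 64%, about 14 points either side. Three of the four rows move by more than that.

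**Is setting the main cause of the shortfall?** The part due to the setting gap is (non-inpatient figure − reported) / (p − reported).
- With c_non = 90%, from (0.855 − 0.779)/(0.95 − 0.779) = 44% to (0.855 − 0.171)/(0.95 − 0.171) = 88%.
- With c_non = 60%, from (0.570 − 0.551)/(0.95 − 0.551) = 5% to (0.570 − 0.114)/(0.95 − 0.114) = 55%.

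The answer depends on inputs the documents do not give.

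**Can the bias reverse?** Let f be the chance of a listed-drug claim in the window for another reason. The reported proportion in one setting is then p × c + (1 − p × c) × f. Take p = 30%, s = 50%, c_IP = 25%, c_non = 90% and f = 30%:
- in hospital: 0.075 + 0.925 × 0.3 = 35.3%
- outside hospital: 0.27 + 0.73 × 0.3 = 48.9%
- overall: 42.1%, above the true 30%

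Reversal is therefore possible when true use is low and unrelated claims are common.

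**The case against.** The strongest reply is that the protocol never says inpatient drug lines are missing. The vial-size category concedes only that the vial is unknown. Table 2 looks for steroids by "code in the IP, non-IP, or pharmacy setting for dexamethasone, methylprednisolone, prednisone, or prednisolone", so some coded inpatient lines are expected. Annex 2's inpatient definition also draws on events in the non-inpatient table. This stands: a reader might infer that inpatient premedication is never itemised, but the documents support only less complete capture as probable.

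A reader might also infer that the proportion mainly reflects care setting. The documents cannot show this. They give no inpatient share or capture rates, and drugs taken without a claim are missed in every setting.

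Nor is understatement certain. Any listed-drug claim in the window counts, and the protocol also treats dexamethasone as a myeloma steroid.

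It can further be said that the row states no denominator, that separate table shells exist but are not shown, that care setting at index is reported anyway, and that no adherence threshold rests on the variable. These points limit the harm. They do not supply a rule for a patient whose premedication cannot be seen. The general provision for reporting missing data does not help, because the flag as defined has only yes and no.

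Finally, dropping all inpatients would discard those who do have a coded claim and shrink a small cohort. That is a fair objection to exclusion, and the change proposed here avoids it.

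**Conclusion.** The point holds as a measurement defect in a primary-objective variable. The flag needs drug-level coding and has no rule for inpatient dosing, although the protocol itself expects inpatient doses of the index drug to lack product detail. Probable consequences are understatement of use and a figure that can shift with the inpatient share between cohorts and refreshes.

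The size is unknown. Over the assumed ranges, an inpatient share rising from 20% to 80% moves the figure by about 6 to 51 points with practice unchanged. The conclusion rests on capture being lower in hospital than outside. The vial-size category and the procedure code make that likely, but nothing states it. Upward bias from unrelated dexamethasone claims cannot be excluded. The point merits a change but does not threaten the study.

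**What to change.** - Report premedication by agent and by care setting of the step-up administrations, not only the setting at index. State how patients with mixed settings are classed, for example as inpatient if any step-up administration was inpatient.
- Make the proportion among non-inpatient step-up patients the main interpretable figure. It will still miss drugs that leave no claim.
- Among inpatients, count those with a coded claim as yes and show the rest as not ascertainable, not as no.
- Add a sensitivity analysis limited to premedication claims on, or the day before, an administration date. For the first dose this reaches one day before index, which the present window excludes, so the definition must say so.
- State the inpatient-capture limitation in Section 9.9.

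The cost is a few extra rows in one table and smaller denominators per stratum, which matter in a cohort of this size. The administration claims already carry the setting, so no new data are needed.

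### The step-up and maintenance averages of time between doses leave out intervals that cross Day 8 or Day 168, so they understate delay; only the whole-follow-up average contains those intervals

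*Protocol*

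**What the plan says.** Protocol section 9.3, Table 3, lists the average time between elranatamab claims under Objective 2, a primary objective. The numerator is the sum of days between claims for the index drug. This is "divided by the total number of administrations -1 reported among patients with 2 or more administrations".

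The assessment periods for the row are "Index date to the end of follow-up Step-Up Dosing Period Maintenance Periods". The row above it uses the same periods and reports the "Proportion of patients with 2 or more administrations of elranatamab during the assessment period", so the two-dose condition is counted within each period.

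Section 9.7.2, Table 4, sets the elranatamab windows. Step-up is "Index date - Day 8", with "3 during Step-Up" expected. Maintenance Period 1 runs from Day 9 to Day 168 with weekly dosing. Maintenance Period 2 runs from Day 169 to censoring with "1 every two weeks". Table 5 ends the teclistamab step-up at Day 7, followed by a single maintenance period. The text below Table 5 says that the dosing outcomes, average time between claims among them, "will be assessed during the above time periods regardless of whether the number of administrations during the period matches the number indicated on the label". The windows therefore stay fixed whatever the patient's actual dosing.

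Neither section says which period an interval belongs to when its two claims fall on opposite sides of a boundary.

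**The concern.** With k doses in a window, a divisor of k − 1 matches exactly the intervals that have both ends in that window. An interval that starts in step-up and ends in maintenance, or that spans Day 168, then belongs to no dosing period. Those are the points where a held or late dose would lengthen an interval most visibly.

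The period averages are there to show where dosing departs from the expected schedule. If long intervals are removed because they are long enough to cross a boundary, the averages lean towards the schedule. In step-up, a delay can even make dosing look faster. No test, error rate or sample size is affected; what is at stake is the accuracy of a descriptive result for a primary objective.

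**Working it through.** The protocol gives no value for this variable, so there is no figure to reproduce. The check applies the Table 3 formula to example dose histories.

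**Inputs from the protocol.** The formula (Table 3) and the windows Day 1–8, Day 9–168 and Day 169 onward (Table 4).

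**Assumptions.** Index is Day 1. On-time doses fall on Days 1, 4 and 8, then weekly from Day 15 to Day 162, then six two-weekly doses on Days 176 to 246.

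**Formula.** Consecutive intervals sum to last day minus first day, so the average is (last − first)/(k − 1).

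**Ceiling on the step-up average.**
- Three doses in the window: (8 − 1)/2 = 3.5 days. Two doses: (8 − 1)/1 = 7 days.
- Teclistamab, with the window ending on Day 7: (7 − 1)/2 = 3 days and 7 − 1 = 6 days.
- If index is counted as Day 0, the elranatamab ceilings are 4 and 8 days.

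**On-schedule patient.** Step-up (8 − 1)/2 = 3.5; Maintenance 1 (162 − 15)/21 = 7.0; Maintenance 2 (246 − 176)/5 = 14.0; whole follow-up (246 − 1)/30 = 8.17.

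**Departures from schedule** (later doses then follow the weekly and two-weekly pattern):

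| History | Step-up | Maint. 1 | Maint. 2 | Whole follow-up |
|---|---|---|---|---|
| On schedule | 3.5 | 7.0 | 14.0 | 8.17 |
| Third dose on Day 15 | 3.0 | 7.0 | 14.0 | 8.45 |
| Third dose on Day 29 | 3.0 | 7.0 | 14.0 | 9.07 |
| Second dose on Day 11, third on Day 15 | none (one dose) | 6.86 | 14.0 | 8.45 |
| First maintenance dose on Day 36 | 3.5 | 7.0 | 14.0 | 9.07 |
| 42-day interval across Day 168 | 3.5 | 7.0 | 14.0 | 9.10 |
| Second dose on Day 7, third on Day 11 | 6.0 | 7.0 | 14.0 | 8.27 |
| Second dose on Day 8, third on Day 12 | 7.0 | 7.0 | 14.0 | 8.30 |

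In rows two and three the only step-up interval left is Day 1 to Day 4, hence (4 − 1)/1 = 3.0. Rows five and six match the on-schedule patient in every dosing period. The last two rows show that a delay ending by Day 8 does raise the step-up average. In each history, two intervals enter no dosing period, and all intervals enter the whole-follow-up average.

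**Dilution in the whole-follow-up average.** For a patient followed only to Day 162, a 28-day interval after Day 8 moves it from (162 − 1)/24 = 6.7 to (162 − 1)/21 = 7.7 days.

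**Illustration at cohort level (assumed rates).** Suppose each step-up interval is delayed with probability p by a whole number of days, uniform on 1 to 14 (mean 7.5).
- True mean interval: 3.5 + 7.5p = 4.3, 5.0 and 6.5 days for p = 0.1, 0.2 and 0.4.
- Patients dropped: the second dose passes Day 8 if its delay exceeds 4 days, so p × 10/14 = 7%, 14% and 29%.
- Reported step-up mean: [3.5(1 − p)² + 3.0p(1 − p) + 5.5p × 4/14] / (1 − p × 10/14) = 3.5, 3.5 and 3.7 days. Here 5.5 is the mean of 4, 5, 6 and 7, the averages when the second dose is 1 to 4 days late and the third falls outside the window.

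Similarly, if 10%, 30% or 50% of patients have a 28-day rather than a 7-day interval into maintenance, its mean is 9.1, 13.3 or 17.5 days (for example 0.9 × 7 + 0.1 × 28 = 9.1). It appears in neither adjacent period average.

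**The case against.** Three stronger readings are tempting, and the protocol supports none of them.

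- **That crossing intervals are counted nowhere.** The same Table 3 row also covers the whole of follow-up, and that average contains every interval up to censoring.
- **That the step-up average cannot show delay.** A second dose that is late but given by Day 8 raises it to as much as 7 days.
- **That a cohort with frequent holds would be reported as on schedule.** Claim counts and relative administration intensity are reported by the same periods. With the first maintenance dose on Day 36, Maintenance 1 doses fall from 22 to 19. Against 160/7 = 22.9 expected, the intensity falls from 0.96 to 0.83. Cut at the last dose on Day 162 (154/7 = 22 expected), it falls from 1.00 to 0.86. The row on patients with two or more administrations also discloses how many patients drop out of the step-up average.

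It can further be said that the exclusion is inferred, that an allocation rule is a detail for an analysis plan, and that fixed label-based windows are deliberate. The first is true: the within-window reading is the natural one but is not stated. The second carries less weight, because the protocol itself sets the formula, the divisor and the windows, and the bias follows from those. The third is fair, but fixed windows do not require crossing intervals to be discarded. The companion measures show that something happened without correcting the interval averages.

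**Conclusion.** The point holds for the period-specific averages only. On the within-window reading, an interval crossing Day 8 or Day 168 (Day 7 for teclistamab) enters no dosing-period average, and those averages understate delay. In step-up, a third dose after the window shortens the average (3.0 against 3.5 days) and a second dose after it removes the patient. The whole-follow-up average contains the delay but dilutes it, cannot locate it, and mixes weekly with two-weekly dosing.

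The ceilings of 3.5 and 7 days depend only on the window and on index being Day 1. The example histories rest on the assumed dose days. The cohort figures rest on assumed delay rates, so they illustrate the mechanism and do not estimate its size in this study. If crossing intervals were meant to be kept, the missing allocation rule would still let two programmers produce different results. The definition should be changed.

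**What to change.** In Table 3 and section 9.7.2:

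1. Report the step-up intervals by dose order (dose 1 to 2, dose 2 to 3), whatever day the later dose falls on.
2. Report the interval from the last step-up dose to the first maintenance dose on its own line.
3. Assign an interval that crosses Day 168 to the period in which it starts.
4. Divide by the number of intervals so assigned, counting each interval once.
5. Leave the whole-follow-up average unchanged.

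Item 2 is needed because assigning every interval to its starting period would put the 7-day step into maintenance inside step-up, raising the on-schedule average from 3.5 to (3 + 4 + 7)/3 = 4.67 days. With the fix, a third dose on Day 15 shows as an 11-day dose 2-to-3 interval instead of 4, and a first maintenance dose on Day 36 shows as 28 days instead of 7.

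The cost is minor reprogramming and no new data. Intervals will look longer and more variable. On the assumed schedule, the on-time Maintenance 1 average becomes (21 × 7 + 14)/22 = 7.3 days, because it now includes the first two-weekly interval; a table footnote should say so. Kaplan-Meier time to next dose, which would keep patients still waiting at censoring, is an optional addition.
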